5.2.1.1 The starting dose will be dose level -1.

Table 1. Dose levels of 5-azacytidine and lirilumab during the lead-in phase (part a)

Dose level	5-azacytidine (mg/m ² /d, Days 1-7)	Lirilumab (mg/kg, day 8)
-4	25	0.3
-3	50	0.3
-2	75	0.3
-1	75	1.0 (Starting dose)
0	75	3.0

5.2.1.2 The goal of the lead-in phase is to identify the dose at which <2/6 patients experience DLT. During the lead-in phase the dose’s of 5-azacytidine and lirilumab may be reduced if 2 or more patients experience DLT at any given dose. After the lead in phase the dose of lirilumab may not be reduced in the phase II portion of the study. For potential lirilumab related AEs in the phase II portion of the study only dose interruptions of lirilumab will be permitted. Dose reductions or escalations of 5-azacytidine will continue to be permitted in the phase II portion of the study and dose reductions or escalations of 5-azacytidine beyond those mentioned in table 5 or different to the doses specified should be discussed with the PI and documentation of the justification recorded in the chart.

5.2.1.3 The dose and /or schedule of administration is subject to modification pending information from ongoing clinical trials of lirilumab as a single agent and in combination with other drugs.

DLT is defined as clinically significant non-hematologic adverse event or abnormal laboratory value assessed as unrelated to disease progression, intercurrent illness, or concomitant medications and occurring during the first cycle on study that meets any of the following criteria:

- CTCAE Grade 3 AST (SGOT) or ALT (SGPT) for ≥ 7 days
- CTCAE Grade 4 AST (SGOT) or ALT (SGPT) of any duration
- All other clinically significant non-hematological adverse event that is Grade 3 or 4 according to the NCI common terminology criteria version 4.0 with the following exceptions:
 - Grade 3 or 4 nausea, vomiting and diarrhea will be considered DLT only if not controlled by optimal therapy.
 - Grade 3 biochemical abnormalities (e.g., lipase or bilirubin elevation) will only be considered DLT if accompanied by clinical consequences. Grade 3 or 4 electrolyte abnormalities will only be considered DLT if possibly related to study drug and not corrected by optimal replacement therapy.

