5.2.1.4 We will first treat 6 patients at dose level -1 in the lead-in phase. If DLT occurs in $\geq 2/6$ patients, this dose level would exceed the MTD, and 6 patients will be treated at the next lower dose level (i.e. dose level -2). If DLT is observed in the first 28 days of treatment in 0 or 1/6 at dose level -1, then dose level 0 will be evaluated. The dose adjustment (Table 1) will continue in cohorts of 6 until we reach a dose level at which $< 2/6$ patients experience a DLT in the first 28 days. The dose level at which 0-1/6 patients experience a DLT in the first 28 days of treatment will be the MTD and will be used to treat an additional 34 patients in the phase II portion of the study. If $\geq 2/6$ patients experience DLT at dose level -4, the study will be revised to consider additional lower dose levels (based on potential synergistic toxicity).

5.2.1.5 Patients that are removed from study before day 28 for any reason other than toxicity and have not experienced DLT will be replaced.

5.2.2 One cycle of therapy is defined as 28 days. Patients will receive one cycle of therapy every 28 days (+/- 7 days).

5.2.2.1 In the phase II part of the study (once the MTD dose has been defined) cycles may be started early (but not earlier than day 21) for patients with active disease if judged in the best interest of the patient.

For the lead-in cohort, DLT defining period is 28 days. As such, cycle 2 should not be started before 28 days for the patients being treated on the lead-in cohort.

5.2.2.2 Subsequent cycles may be delayed for recovery of toxicity or other medical conditions (e.g. infections). Delays in start of subsequent cycles greater than 8 weeks will be acceptable only for patients who are deriving clinical benefit and after discussion with the principal investigator of potential risk/benefit ratio.

5.2.2.3 In instances where one drug has to be discontinued transiently because of safety, the administration of the other drug may continue as scheduled. If the drug that is held can resume at a later time, no doses will be made up and the administration will follow the originally defined schedule calendar according to the drug that was continued.

5.2.2.4 Subsequent courses of 5-azacytidine and lirilumab may be administered regardless of peripheral blood counts during the first 4 cycles and/or in the presence of residual leukemia.

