11.2 Statistical Design

Part a. Lead-in phase

The MTD is defined as the highest dose level with ≤ 1 out of 6 patients experience a DLT during the first 28 days of treatment. DLT is defined in section 5.2.2. The dosing schema for the combination treatment during the lead in phase is shown in Table 1 in section 5.2.1.

Part b. Phase II

Historical data on similar patients shows an ORR of 10-15%. The target ORR with the experimental treatment is 30%. This regimen of the combination treatment will be considered worthy of further investigation if it elicits an increase in ORR to 30% with acceptable toxicity. A $>30\%$ drug-related grade 3/4 toxicity rate is considered unacceptable. Thus, interim monitoring rules, assuming the prior distributions above, were constructed that meet the following two conditions,

- 1) Stop if $\text{Prob}\{p(\text{ORR}, E) < p(\text{ORR}, H) + 0.15 \mid \text{data}\} > 0.975$, or
- 2) Stop if $\text{Prob}\{p(\text{TOX}, E) > 0.30 \mid \text{data}\} > 0.975$,

where $P(\text{ORR}, E)$ and $P(\text{TOX}, E)$ are the true ORR and toxicity rates for the combination treatment, and $p(\text{ORR}, H)$ is the true ORR rate of the standard treatment. The first rule provides for stopping the study if the data suggest that it is unlikely (i.e., probability $< 2.5\%$) that ORR rate of the combination treatment is greater than the ORR rate of standard treatment by 15.0%. The second condition will stop the study early if excessive therapy-related grade 3/4 toxicity ($>30\%$) is highly probable (i.e., probability $>97.5\%$) for the combination treatment. Monitoring for toxicity and futility will not begin until 5 patients have been evaluated, and cohort size for future evaluations is 5.

The monitoring rule for the toxicity rate, based on these assumptions and monitoring conditions above is found in Table 4. **For example, accrual will cease if 4 or more patients experience toxicities among the first 5 patients.**

Table 4. Stop accrual if the number of drug-related grade 3/4 toxicities is greater than or equal

to indicated (i.e., # patients with toxicities) among the number of patients evaluated								
# patients evaluated	5	10	15	20	25	30	35	40
# patients with toxicities	4-5	6-10	8-15	10-20	12-25	14-30	16-35	Always stop with this many patients

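### The general DLT criterion stops at Grade 4, so a cycle-1 non-hematologic drug toxicity recorded only as Grade 5 adds nothing to the count that sets the MTD

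*Combined protocol and SAP*

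**What the plan says.** Section 5.2.1.3 opens its definition with "DLT is defined as clinically significant non-hematologic adverse event or abnormal laboratory value". The event must occur in the first cycle and be judged unrelated to progression, intercurrent illness or concomitant medication, and it must then meet one of three criteria:

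- "CTCAE Grade 3 AST (SGOT) or ALT (SGPT) for" at least seven days;
- "CTCAE Grade 4 AST (SGOT) or ALT (SGPT) of any duration";
- "All other clinically significant non-hematological adverse event that is Grade 3 or 4", with exceptions that only narrow it (gastrointestinal events controlled by treatment, certain biochemical and electrolyte abnormalities).

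The count that follows is in 5.2.1.4: "The dose level at which 0-1/6 patients experience a DLT in the first 28 days of treatment will be the MTD". That level is then used for 34 further patients. Section 11.2 words it as "The MTD is defined as the highest dose level with" at most one DLT among six. On replacement, 5.2.1.5 says: "Patients that are removed from study before day 28 for any reason other than toxicity and have not experienced DLT will be replaced".

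Three other places bear on the grade wording. Section 2.4 reports two Grade 5 events in the AML maintenance trial separately from its Grade 3 and 4 events. Section 5.3.6, on re-escalation of 5-azacytidine, refers to non-hematologic drug-related toxicity of Grade 3 and above. In 11.2, the Phase II toxicity rule and Table 4 count drug-related Grade 3/4 toxicities.

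**The concern.** Section 1.1 makes the MTD and DLT the primary objective of the lead-in, and the count of DLTs among six patients is the only numerical rule that selects the dose. The most serious grade is the one the general criterion leaves out. A patient lost to drug toxicity has not left for a reason other than toxicity, so 5.2.1.5 gives no ground for replacement. If the event carries only Grade 5, the patient remains in the denominator of six and adds nothing to the numerator.

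The wording cannot be taken as house shorthand for Grade 3 and above, because 5.3.6 uses an open-ended form and 2.4 treats Grade 5 as its own category. Nor does the Phase II monitoring rule supply the missing count, since it has the same upper limit.

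**Working it through.** **What is being checked.** The documents give no operating characteristics for the lead-in rule, so there is no stated figure to reproduce. The check traces one patient through the rules and then sizes the effect with the exact binomial.

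**Tracing the rules.** Take a drug-related, non-hematologic event in cycle 1.

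| How the event is recorded | Meets 5.2.1.3? | Replaced under 5.2.1.5? | Effect on the count of six |
|---|---|---|---|
| Qualifying Grade 3 or 4, patient survives | Yes | No | One DLT |
| Qualifying Grade 3 or 4, later fatal | Yes, already met | No | One DLT |
| Grade 5 only | No | No, on the natural reading | Counted as no DLT |

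The gap is the last row only.

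**Size.** Inputs from the documents: six patients per level, and a level passes with 0 or 1 DLTs (5.2.1.4, 11.2). Inputs assumed: the true DLT rate p with fatal events included; the share f of dose-limiting events that are fatal; and the proportion u of those fatal events with no separately recorded qualifying Grade 3/4 event.

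The rate that the written rule sees is p' = p × (1 − f × u), and

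P(pass) = (1 − p')^6 + 6 p' (1 − p')^5.

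With p = 0.30:

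- All events counted: p' = 0.30. P = 0.1176 + 0.3025 = 0.420.
- f = 0.10, u = 1: p' = 0.30 × 0.90 = 0.27. P = 0.1513 + 0.3358 = 0.487.
- f = 0.10, u = 0.5: p' = 0.30 × 0.95 = 0.285. P = 0.1336 + 0.3195 = 0.453.

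So for a 10% fatal share the pass probability lies between 42% (every fatal event had a qualifying record) and 49% (none had).

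**The same point without a fixed total.** Let a be the rate of qualifying Grade 3/4 DLTs and q the rate of drug-related deaths recorded only as Grade 5, both assumed. As written, P(pass) depends on a alone. At a = 0.10 it is 0.9^6 + 6 × 0.1 × 0.9^5 = 0.886, whatever q is. If Grade 5 counted, the rate would be a + q. At q = 0.05 that is 0.85^6 + 6 × 0.15 × 0.85^5 = 0.776; at q = 0.10 it is 0.8^6 + 6 × 0.2 × 0.8^5 = 0.655. The written count does not respond to deaths of this kind.

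**The case against.** A reader might infer that no drug-related death in cycle 1 is a DLT. The documents do not support that. The rule counts patients who experience a DLT, and an event that reached a qualifying Grade 3 or 4 has met the definition; nothing cancels it if the patient later dies. This objection stands, and it makes the 49% an upper bound for the assumed fatal share.

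A reader might also infer that a lethal dose level could go forward unchecked. It could not. Section 5.2 requires the IND office Medical Monitor to approve the cohort summary before the next level opens. Section 9.2 allows the study to be terminated for severe adverse reactions. Sections 10.4 and 10.5 require prompt reporting: fatal events that are unexpected and drug-related within 24 hours to the IND office, and all SAEs within 24 hours to the drug supplier. These make adoption of such a level unlikely. They are matters of judgement or reporting, however, and none turns a Grade 5 event into a DLT or alters the count.

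Larger effects are easy to generate: fatal shares of 20% or 30%, all unrecorded at lower grade, give p' = 0.24 or 0.21 and pass probabilities of 56% or 63%. The documents offer no basis for such shares. Section 2.4 reports no DLTs in the monotherapy dose escalation, and two Grade 5 events among 150 subjects in the maintenance trial, both judged unrelated to study drug. Those data concern neither this combination nor this population, so they do not settle the share either.

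Finally, 5.2.1.5 speaks of removal from study and does not say how a death is classed. That the patient stays in the six is the natural reading, not an explicit statement.

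**Conclusion.** The point holds in a limited form. The written criterion omits drug-related non-hematologic events recorded only as Grade 5, and the MTD count then treats that patient as DLT-free. The Phase II toxicity count has the same omission, and 5.3.6 shows that the protocol does not use one grade convention throughout.

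The effect on the lead-in rule is modest under the illustrative assumption: a pass probability of up to 49%, and about 45% if half the deaths have a qualifying record, against 42% at a true 30% DLT rate. The fatal share and the recorded proportion are both assumptions. The case for change rests less on that size than on the fact that a pre-specified count should not depend on readers departing from it for the gravest outcome.

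Hematologic deaths are a related but separate matter. The opening of the definition excludes hematologic events, although 5.3.6 mentions a hematologic DLT, so extending the grade range of the non-hematologic criterion would not bring them in. This should be corrected, but it does not undermine the design as a whole.

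**What to change.** Reconcile the grade wording in 5.2.1.3, 5.3.6 and 11.2 (the stopping rule and Table 4) so that Grade 5 events are included in both the DLT tally and the Phase II toxicity count. The open-ended wording already in 5.3.6 would serve. Keep the attribution wording of 5.2.1.3 as it stands. A looser test for deaths of uncertain cause would be a new clinical rule, and this point gives no ground for one.

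The sponsor should also state how deaths before day 28 are classed for 5.2.1.5 and for the count of six, including hematologic deaths, and reconcile the reference in 5.3.6 to a hematologic DLT with the non-hematologic definition.

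The cost is a phrase in 5.2.1.3, matching edits in 11.2 and Table 4, and a sentence on deaths. Sample size, cohort size and the numerical boundaries are unchanged.

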5.3.4 Lirilumab Discontinuation Criteria

Treatment should be permanently discontinued for the following:

- Any Grade 2 drug-related uveitis or eye pain or blurred vision that does not respond to topical therapy and does not improve to Grade 1 severity within the re-treatment period OR lasting > 7 days with systemic treatment
- Any Grade 3 non-skin, drug-related adverse event lasting > 7 days, with the following exceptions for drug-related laboratory abnormalities, uveitis,

pneumonitis, bronchospasm, diarrhea, colitis, neurologic adverse event, hypersensitivity reactions, and infusion reactions:

- Grade 3 drug-related uveitis, pneumonitis, bronchospasm, diarrhea, colitis, neurologic adverse event, hypersensitivity reaction, or infusion reaction of any duration requires discontinuation
- Grade 3 drug-related laboratory abnormalities do not require treatment discontinuation except those noted below:
- Any drug-related liver function test (LFT) abnormality that meets the following criteria require discontinuation: AST or ALT > 8 x ULN
- Any Grade 4 drug-related adverse event or laboratory abnormality, except for the following events which do not require discontinuation:
 - Isolated Grade 4 amylase or lipase abnormalities that are not associated with symptoms or clinical manifestations of pancreatitis and decrease to < Grade 4 within 1 week of onset.
 - Isolated Grade 4 electrolyte imbalances/abnormalities that are not associated with clinical sequelae and are corrected with supplementation/appropriate management within 72 hours of their onset
- Any dosing interruption lasting > 8 weeks with the following exceptions:
 - Dosing interruptions to allow for prolonged steroid tapers to manage drug-related adverse events are allowed. Prior to re-initiating treatment in a subject with a dosing interruption lasting > 8 weeks the Investigator must be consulted. Tumor/Leukemia assessments should continue as per protocol even if dosing is interrupted.
 - Dosing interruptions > 8 weeks that occur for non-drug-related reasons may be allowed if approved by the Investigator. Prior to re-initiating treatment in a subject with a dosing interruption lasting > 8 weeks the Investigator must be consulted. Tumor/Leukemia assessments should continue as per protocol even if dosing is interrupted.

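### Some cycle-1 events that require permanent lirilumab discontinuation under 5.3.4 are not DLTs, so the 0–1 of 6 rule can clear a dose at which patients had to stop the drug

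*Combined protocol and SAP*

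**What the plan says.** Section 5.2.1.3 confines DLTs to clinically significant non-hematologic events or laboratory values in the first cycle. The general criterion is "All other clinically significant non-hematological adverse event that is Grade 3 or 4". Several events are then carved out. For gastrointestinal events, "Grade 3 or 4 nausea, vomiting and diarrhea will be considered DLT only if not controlled by optimal therapy". For electrolytes, "Grade 3 or 4 electrolyte abnormalities will only be considered DLT if possibly related to study drug and not corrected by optimal replacement therapy". For transaminases below Grade 4, the criterion is "CTCAE Grade 3 AST (SGOT) or ALT (SGPT) for ≥ 7 days".

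Section 5.3.4 lists reasons to stop lirilumab permanently. One reads "Grade 3 drug-related uveitis, pneumonitis, bronchospasm, diarrhea, colitis, neurologic adverse event, hypersensitivity reaction, or infusion reaction of any duration requires discontinuation". Another begins "Any Grade 2 drug-related uveitis or eye pain or blurred vision that does not respond to topical therapy" and has an alternative branch for events that last more than 7 days with systemic treatment. All drug-related Grade 4 events are included, apart from isolated amylase or lipase findings and isolated electrolyte findings. The electrolyte exemption applies only if there are no clinical sequelae and correction takes place within 72 hours. Liver tests "require discontinuation: AST or ALT > 8 x ULN".

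Sections 5.2.1.4 and 11.2 set the MTD from the number of DLTs among six patients in the first 28 days: 0 or 1 passes. Section 5.2.1.5 adds: "Patients that are removed from study before day 28 for any reason other than toxicity and have not experienced DLT will be replaced".

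Table 2 in 5.3.2 covers Grade 3 or 4 non-hematologic drug-related events. It has lirilumab held and then resumed at the prior dose, even at a fifth occurrence.

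**The concern.** The two lists classify the same event differently. One treats it as serious enough to end the investigational drug for that patient; the other treats it as tolerable when the dose is judged. Nothing in the plan makes permanent discontinuation for toxicity a DLT, and nothing says how such a patient should be read in the 0–1 of 6 count.

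The lead-in exists to show that the combination is tolerated, and its result carries forward. The selected dose is used for a further 34 patients (5.2.1.4), lirilumab cannot be reduced in phase II (5.2.1.2), and lead-in patients on lower doses may be moved up to the MTD (11.1). A count that leaves out treatment-ending toxicity makes a dose look better tolerated than it was.

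**Working it through.** The plan states no operating characteristic for the lead-in rule, so there is no figure to reproduce. The check compares the two lists and then gives an illustration.

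**Step 1: the lists side by side (drug-related events in cycle 1).**

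| Event | 5.3.4, lirilumab | 5.2.1.3 |
|---|---|---|
| Grade 3 diarrhea, controlled | Permanent stop, no duration condition | Not a DLT |
| Grade 4 diarrhea or vomiting, controlled | Permanent stop; neither Grade 4 exception applies | Not a DLT |
| Grade 2 uveitis, eye pain or blurred vision, over 7 days on systemic treatment | Permanent stop | Not a DLT; below Grade 3 |
| Grade 4 electrolyte abnormality, corrected only after 72 hours | Permanent stop; outside the exemption | Not a DLT once corrected; no time limit |
| AST or ALT above 8 × ULN, under 7 days | Permanent stop | Not a DLT only if still Grade 3 |

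The first four rows follow from the text. The last holds only if CTCAE Grade 3 extends above 8 × ULN. That is an assumption, because Appendix C is listed but not reproduced, and the conclusion does not use it.

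Timing allows these events to fall in the DLT window. Lirilumab is given on Day 8 ± 2, which leaves 28 − 10 = 18 to 28 − 6 = 22 days. The other branch of the eye criterion refers to a re-treatment period that is not defined. Under 5.3.3 the next lirilumab dose is on Day 8 of the next cycle, so that branch may resolve only after the window; it is not relied on.

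**Step 2: how the patient enters the count.** A patient who stops only lirilumab normally stays on study (9.1.4), so 5.2.1.5 does not apply. A patient removed from study for toxicity is not replaced. Either way the patient is one of the six and has no DLT. In the limit, six of six could stop lirilumab permanently with 0 of 6 DLTs, and the rule would be met.

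**Step 3: illustration.** Let *d* be the DLT rate and *q* the proportion of patients with a forced stop but no DLT. Both are assumed, and patients are taken as independent. The chance of clearing a level is

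P(X ≤ 1 of 6) = (1 − p)⁶ + 6p(1 − p)⁵ = (1 − p)⁵(1 + 5p),

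with p = d as written and p = d + q if forced stops counted. Take d = 10%. As written, 0.9⁵ × 1.5 = 0.8857, whatever q is.

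| q | p if counted | Chance of clearing if counted | Difference from 88.6% (unrounded values, points) |
|---|---|---|---|
| 2% | 0.12 | 0.88⁵ × 1.60 = 84.4% | 4.1 |
| 5% | 0.15 | 0.85⁵ × 1.75 = 77.6% | 10.9 |
| 10% | 0.20 | 0.80⁵ × 2.00 = 65.5% | 23.0 |
| 20% | 0.30 | 0.70⁵ × 2.50 = 42.0% | 46.6 |

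The last column is the chance that a level passes as written but would fail if forced stops counted.

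**The case against.** **Different purposes.** A DLT rule judges a dose and a discontinuation rule protects one patient, so the lists need not coincide. That is fair in principle. The plan, however, gives no reason for the differences and does not say how the patients who fall between the lists are read.

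**The stop may not be mandatory.** Table 2 lets lirilumab resume after Grade 3–4 non-hematologic events. Section 5.3.7.4 also allows only the drug judged responsible to be adjusted, so a gastrointestinal event attributed to 5-azacytidine need not end lirilumab. Both points narrow the affected group. The first is also a conflict within section 5.3, and it enlarges what has to be reconciled.

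**The replacement rule.** A reader might take 5.2.1.5 as the defect. It is not. A patient stopped for lirilumab toxicity in cycle 1 has already had that cycle's single dose and can be evaluated, and keeping toxicity removals in the six is the cautious choice. What is missing is how they are classified.

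**Safeguards.** The Medical Monitor must approve the cohort summary before a dose advance (5.2). Phase II monitors drug-related Grade 3/4 toxicity with no stated exemption for controlled events (11.2), and it includes the six MTD patients (11.1). Table 4 stops accrual at 4 of the first 5, so the six-of-six extreme would be caught if the events were Grade 3/4. These are real but partial protections. Section 5.2 does not say that the summary must show non-DLT discontinuations. Two or three such events among the first five would not reach the Table 4 boundary, and Grade 2 eye events are not counted at all.

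**Rates.** The only related-event data in the plan point low. In section 2.4, among 150 blinded subjects on lirilumab or placebo, nine had related Grade 3 events, one had a related Grade 4 event, and one discontinued for a related event. None of the related Grade 3 or 4 events listed was diarrhea, vomiting, an eye event or an electrolyte abnormality. Those subjects received at most 1.0 mg/kg and are reported without 5-azacytidine, so the data do not settle the rate here. They do mean that 10% and 20% should be read as the upper part of an assumed range.

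**Conclusion.** The mismatch is real and follows from the text for the four kinds of event in the first four rows of the table. As stated, the MTD rule can clear a dose at which patients had to stop lirilumab permanently under 5.3.4. With an assumed 10% DLT rate, the effect on the chance of clearing a level runs from about 4 percentage points at a 2% forced-stop rate to about 47 at 20%. The documents do not show where in that range the trial would lie.

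Three stronger readings are not supported:

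- A reader might infer that such a dose would pass unexamined to 34 more patients. Medical Monitor approval and the phase II toxicity boundary stand in between, although neither alters the MTD rule.
- The transaminase case might be read as certain. It depends on CTCAE bounds that are not reproduced.
- Drug-related Grade 4 hematologic events might be added, since DLTs are non-hematologic only. Section 5.3.1 says that lirilumab should generally not be discontinued for myelosuppression, so this case is too weak to carry weight.

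This should be corrected, but it does not by itself invalidate the lead-in design. No view is taken on which clinical rule is right.

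**What to change.** The sponsor should reconcile the DLT definition (5.2.1.3), the MTD and replacement rules (5.2.1.4, 5.2.1.5 and the matching text in 11.2), Table 2 (5.3.2) and the discontinuation criteria (5.3.4). It is for the sponsor to decide which rule changes. The text should then say how a lead-in patient who is permanently stopped for toxicity in the first 28 days, without a DLT, enters the 0–1 of 6 count.

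The cohort summary in 5.2 should report the number of such patients at each dose level, beside the DLT count, before the dose decision is made.

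The cost is wording and one extra line in the summary. Reasons for discontinuation are already to be captured (second item numbered 5.2.2.4), so no new data are needed. The possible downside is a more conservative MTD if the sponsor chooses to count these events.
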